9.3 Populations for analyses

Table 15.

Outcome variable	Populations
Efficacy Data	
ORR	Efficacy analysis set (ITT population)
PFS	Efficacy analysis set (ITT population)
OS	Efficacy analysis set (ITT population)
Safety Data	
AEs	Safety analysis set
ECOG performance status	Safety analysis set

AE Adverse events; ORR Overall response rate; PFS Progression free survival; OS Overall survival; ECOG Eastern Cooperative Oncology Group; ITT Intention to treat

All Subject Analysis Set

The All Subject Analysis Set will include information from all screened subjects, including those who did not meet the study entry criteria or did not receive a study treatment. This data set will only be used for disposition in which all screened subjects are accounted for.

Efficacy Analysis Set (ITT population)

The Efficacy Analysis Set will include all subjects who receive any amount of study treatment for efficacy analyses. Efficacy analyses will be based on the actual treatment received. The ORR analysis will be based on subjects who are in the Efficacy Analysis Set and who had disease assessment at baseline and at least 1 follow up disease assessment or subjects who died or

stopped treatment before the first scheduled disease assessment due to clinical progression or toxicity.

Safety Analysis Set

The Safety Analysis Set will include data from all subjects who receive any amount of study drug. Safety analysis will be based on the actual treatment received. All data will be included, and no subjects excluded because of protocol violations.

Schedule of Analysis

This is an open-label study. Ongoing analyses to help manage the study and support the DSMC reviews for safety and antitumor activity will be undertaken. A final analysis will be conducted after all subjects have completed the study.

Disposition

The number and percentage (n, %) of subjects enrolled, treated, lost to follow-up, and withdrawn from treatment or discontinued from the study (with reason) will be summarized. The sample sizes for the Efficacy Analysis Set, Safety Analysis Set will be clearly identified. All subjects in the All Subject Analysis Set will be included in the disposition analysis.

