The study will enroll 30 patients to receive temozolomide + olaparib combination therapy every 3 weeks (q3w). Patients will provide a tumor tissue sample at screening to determine MGMT promoter hypermethylation by methylation-specific polymerase chain reaction (PCR) analysis.

Treatments and treatment duration:

Systemic therapy:

Temozolomide + Olaparib: Temozolomide (75 mg/m² orally on days 1-7 every 3 weeks) + Olaparib (150 mg orally twice daily days 1-21) in a 21-day cycle.

Duration of treatment:

Treatment will continue until disease progression, unacceptable adverse event(s), withdrawal of consent or death.

Progression during treatment:

During the treatment period, patients who have Response Evaluation Criteria in Solid Tumors, version 1.1 (RECIST 1.1) defined radiological progression will proceed to follow-up. Patients with equivocal progression who are clinically stable may continue on treatment phase of the study at the discretion of the patient and Investigator until progression is confirmed, no earlier than 4 weeks after and preferably within 4 to 6 weeks after the prior assessment of progression of disease.

Follow-up of patients post discontinuation of study drug:

Patients who have discontinued study treatment due to toxicity or symptomatic deterioration, clinical progression/recurrence, or who have commenced subsequent anticancer therapy will be followed until RECIST 1.1-defined progression of disease and then at least for an additional 8 weeks with at least 1 additional follow up scan or death (whichever comes first). A repeat optional tumor biopsy will be done at the time of disease progression unless it is deemed clinically unsafe to perform.

Survival:

All patients in the study should be followed up for survival.

Independent data monitoring committee:

The principal investigator and Yale Center for Clinical Investigation (YCCI) are responsible for monitoring the performance of the study. The Yale Cancer Center Data and Safety Monitoring Committee (DSMC) will provide primary oversight of data and safety monitoring. The Yale DSMC will review and monitor compliance, toxicity and deviations from this study. The committee is composed of clinical specialists with experience in oncology and who have no direct relationship with the study. Information that raises any questions about participant safety will be addressed with the Principal Investigator. The DSMC will review this protocol at a minimum of once every six months.

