4.2 Safety Evaluation Period

A safety evaluation period to assess for dose limiting toxicity (DLT) will be employed for at least the first 6 treated patients. Should excessive toxicity be observed at the starting dose, a dose de-escalation schema will be used for TMZ to 60 mg/m², while the olaparib will be maintained at the specified dose of 150 mg twice daily. Patients will be enrolled in cohorts of 3 during the safety evaluation period. For the first 3 patients treated on the study with olaparib 150 mg twice daily and TMZ 75 mg/m², if $\leq 1/3$ DLTs are observed, 3 additional patients will be enrolled at this dose and if $\leq 1/6$ DLTs are seen enrolment will proceed at this dose. If 2 or more DLTs are observed in either the first 3 or 6 patients treated at the starting doses, the TMZ dose will be decreased to 60 mg/m² with olaparib 150 mg twice daily. If 2 or more DLTs are seen in either the first 3 or 6 patients treated at TMZ 60 mg/m² with olaparib 150 mg twice daily then a further dose reduction to TMZ 50 mg/m² with olaparib 150 mg twice daily will be done. The doses of TMZ 50 mg/m² D1-7 with olaparib 150 mg twice daily have previously been tested as outlined in section 4.5. Therefore if the starting doses require reduction to TMZ 50 mg/m² D1-7 with olaparib 150 mg twice daily then safety will be assessed per the data safety monitoring plan as outlined in section 9.5.2.

The dose management tables throughout the protocol will be adjusted in an amendment as necessary if an alternate starting dose is identified. If a dose reduction is necessary, at least 9 patients (per early stopping rule) and up to 30 evaluable patients will be treated at the reduced dose as part of the efficacy analysis. Therefore in the case of a dose reduction the enrolment of 30 patients will be maintained at the same dose.

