9.2 Sample size determination

The sample size estimation for the single-arm of this phase II study is based on the primary endpoint of objective response rate (ORR). The protocol plans to enroll a total of 30 evaluable patients at the recommended dose level in a single-arm open label phase 2 study Simon's Two-Stage optimal design. There will be screening for eligibility and we will examine several secondary endpoints. Patients will be considered evaluable for the primary endpoint if they complete at least 1 cycle of study treatment followed by response assessment imaging. Patients that are not evaluable may be replaced to ensure the appropriate number of evaluable patients is enrolled as outlined in the sample size determination for the primary endpoint in the Simon's two-stage optimal design described below.

Screen: To be eligible for this trial, patients will first need to be screened for the MGMT promoter hypermethylation and/or MGMT lack of expression. We anticipate at least 20% of those screened will exhibit an appropriate biomarker as well as meet eligibility criteria. To obtain 30 eligible patients, the mean number of patients to be screened is 150. Using the negative binomial distribution as reference, there is a 6% probability more than 190 subjects will need to be screened to attain the 30 eligible patients.

The **primary endpoint** is the objective response rate to the combined therapy and will be assessed in a Simon's two-stage optimal design. Published, historical records anticipate a response rate of 5% or lower and we will assume a null hypothesis of 5%. We will reject this null hypothesis in favor of a higher rate if we observe 4 or more responses in the evaluable patient sample of 30. Patients will be considered evaluable for the primary endpoint if they complete at least 1 cycle of study treatment with response assessment imaging. The trial will terminate early if we do not observe 1 or more responses in the first 9 evaluable patients. The probability of 4 or more responses in a sample of 30 has probability .049, which is the significance level. If the true, underlying response rate is 25% or greater, then this trial has power 90%. The expected sample size is 17 under the null hypothesis. There is a 63% chance of stopping early under the null hypothesis.

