9.4.1 Efficacy analyses

Primary Endpoint: Overall response rate (ORR) by RECIST v1.1 criteria for combined therapy of olaparib and temozolomide.

Analytic Plan for Primary Endpoint:

The objective response is defined as a complete or partial response, as determined by investigator assessment using RECIST v 1.1 and confirmed by repeated assessment > 4 weeks after initial documentation. Patients with missing or no response assessments are classified as non-responders. The trial will terminate early if we do not observe 1 or more responses in the first 9 evaluable patients. The ORR will be estimated using the 95% confidence interval (CI) based on Wilson's method. A 5% 2-sided alpha will be used.

Secondary Endpoints: PFS, OS, Safety

Analysis Plans for Secondary Endpoints:

Secondary endpoints include overall survival, progression-free survival, and toxicity. Survival endpoints will be plotted using the Kaplan-Meier, product-limit method and compared across clinical measurements using Cox proportional hazards regression. Time to progression begins at the time of initial treatment and ends at the earliest of withdrawal, diagnosed progression, or death. For PFS subjects who are alive and have not progressed will be censored at the date of

their last RECIST tumor assessment. For OS subjects who are alive will be censored at the date of their last survival assessment. Toxicity rates will be compared to established rates for these treatments and summarized using means and 95% confidence intervals.

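### Section 9.3 puts patients from every dose level in the primary ORR set, while 4.2 and 9.2 tie the 4-of-30 rule to one level; after a de-escalation the primary analysis is ambiguous

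*Combined protocol and SAP*

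**What the plan says.** - **Section 9.3** assigns ORR to the Efficacy Analysis Set, labelled the ITT population: "The Efficacy Analysis Set will include all subjects who receive any amount of study treatment for efficacy analyses". It narrows the ORR analysis to patients with a baseline and at least one follow-up assessment, or who died or stopped before the first scan because of clinical progression or toxicity. Dose level is not mentioned.
- **Section 9.4** says that the primary and secondary endpoints are analysed by intention to treat.
- **Section 4.2**, on what happens after a dose reduction: at least 9 (citing the early stopping rule) and "up to 30 evaluable patients will be treated at the reduced dose as part of the efficacy analysis". It adds that the enrolment of 30 is kept at the same dose.
- **Section 9.2**: "The protocol plans to enroll a total of 30 evaluable patients at the recommended dose level". The rule of 4 or more is attached to that evaluable sample of 30.
- **Sections 9.2, 9.4.1 and 9.5** describe the futility look as being on the first 9 patients, without naming a dose level.
- **Section 1.2**: "The study will enroll 30 patients to receive temozolomide + olaparib combination therapy". It gives no larger total for the case of a de-escalation.

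**The concern.** After a de-escalation, two analysts could each follow the text and reach different primary results. One working from 9.3 and 9.4 would count responses in everyone treated, including patients at a level that was dropped. A patient who stopped for a dose-limiting toxicity stays in, because the ORR subset in 9.3 explicitly keeps early stops for toxicity. One working from 4.2 and 9.2 would count only the 30 at the level carried forward.

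The threshold of 4 was calibrated for 30 patients, and no threshold is given for any other number. Applied to a larger set it is easier to pass. The estimated ORR would also no longer describe the regimen being taken forward.

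**Working it through.** **Inputs.** Null rate 5%, alternative 25%, stop if 0 of the first 9 respond, success if 4 or more of 30 respond (9.2). Patients left at a dropped level: 3 to 6 at each of up to two levels (4.2).

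**1. Reproduce the plan's figures.** The probability of declaring success with N patients in the final count is

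P(N, p) = Σ over x = 1 to 9 of Bin(x; 9, p) × P(Bin(N − 9, p) ≥ 4 − x).

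At N = 30, p = .05:
- x = 1: .29854 × .08492 = .02535
- x = 2: .06285 × .28303 = .01779
- x = 3: .00772 × .65944 = .00509
- x ≥ 4: .00064

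The sum is .0489. At p = .25 the same formula gives .902. Early stopping under the null is .95^9 = .630, and the expected sample size is 9 + 21 × (1 − .630) = 16.8. All four stated figures reproduce. The .049 is the one-sided error of the two-stage rule; the plain probability of 4 or more in 30 is .061.

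**2. Patients treated after a de-escalation.** One: 30 + (3 to 6) = 33 to 36. Two: 30 + (6 to 12) = 36 to 42. Replacements allowed in 4.3 and 9.2 would add to this. A dropped-level patient outside the ORR subset of 9.3 would reduce the number in the ORR count.

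**3. Type I error if all are pooled in the final count, with the threshold left at 4.** Futility is judged on 9 patients at the final level, as 4.2 indicates, with p = .05 throughout.

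| N | Terms x = 1, 2, 3, ≥ 4 | Type I error | Ratio to .0489 |
|---|---|---|---|
| 30 | .0254 + .0178 + .0051 + .0006 | .049 | 1.00 |
| 33 | .0346 + .0213 + .0055 + .0006 | .062 | 1.27 |
| 36 | .0449 + .0248 + .0058 + .0006 | .076 | 1.56 |
| 42 | .0678 + .0312 + .0063 + .0006 | .106 | 2.17 |

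**4. Agreement with the planned interval.** Section 9.4.1 reports a Wilson 95% interval. Its lower limit is 5.3% for 4/30, 4.8% for 4/33 and 4.4% for 4/36. With three pooled patients, exactly 4 responses would meet the success rule while the interval includes the 5% null.

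**5. How likely the extreme is.** The documents give no DLT rate, so take an assumed rate q, the same at both levels. A level is dropped after 6 patients with probability P(0 of 3) × P(≥ 2 of 3) + P(1 of 3) × P(≥ 1 of 3). At q = 20% this is .512 × .104 + .384 × .488 = .2406, so N = 42 has probability .2406² = .058. At q = 10% and 30% it is .007 and .132. Averaged over all paths, including no de-escalation, the pooled type I error is .052, .060 and .070 for q = 10%, 20% and 30%.

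**6. After the fix.** Restricting the test to the 30 at the final level restores .0489 and .902.

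**The case against.** The best counter-argument is that 4.2 already answers the question. It is the section written for a de-escalation, and it says that patients at the reduced dose form the efficacy analysis. Section 9.2 agrees, and no section applies the threshold of 4 to more than 30. A general set definition that is silent on dose is weaker evidence than a rule made for the case. Section 9.3 also says that efficacy follows the treatment actually received, which could mean by dose level.

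Much of this stands. The intended answer is probably the one in 4.2 and 9.2, and the inflation arises only if 9.3 displaces them with the threshold unchanged. It does not remove the conflict. Section 9.3 is where an analyst looks for the primary set, its definition is inclusive, and 9.4 reinforces it. The sentence on treatment received does not mention dose level, and 9.3 uses nearly the same sentence for the Safety Analysis Set, which plainly holds every treated patient.

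Two stronger readings are tempting and not supported:
- **That the plan doubles its type I error.** Doubling is reached only near 42 patients, with both levels dropped after 6 patients each, and only under the pooled reading.
- **That most or all of the 9 patients at the futility look could be at a dropped level.** Sections 9.2, 9.4.1 and 9.5 omit the dose level, but 4.2 ties the early stopping rule to at least 9 patients at the reduced dose, and nothing counts earlier-level patients towards it.

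The synopsis figure of 30 is a fair base plan, since the synopsis mentions the run-in and possible de-escalation. It is simply not the total after one.

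**Conclusion.** The conflict is real and lies in operative text: the sections disagree on who enters the primary ORR after a de-escalation, and no order of precedence is given. It should be corrected.

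Its size is conditional. With no de-escalation there is no effect. With one, following 9.3 with the threshold at 4 gives a type I error of about .062 to .076 instead of .049; the far end, at 42 patients, is about .106. These figures assume a 5% response rate at every level, futility judged on 9 patients at the final level, and all dropped-level patients in the ORR count. Apart from error rates, the pooled ORR would describe a mixture that includes levels dropped for toxicity.

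**What to change.** - **9.3:** define the primary ORR set as evaluable patients treated at the starting dose level carried forward. Classify patients by assigned starting level, so that individual dose reductions do not move anyone between sets.
- **9.2, 9.4.1 and 9.5:** say that the first 9 are at that same level, consistent with 4.2.
- **Earlier-level patients:** report their responses separately, by level, and keep them in the Safety Analysis Set.
- **9.4:** reconcile the ITT sentence with this set. Give evaluable one meaning, because 9.2 asks for a completed cycle with imaging while 9.3 keeps patients who stopped earlier for progression or toxicity.
- **1.2:** restate enrolment as 30 evaluable at the final level, plus 3 to 6 patients per dropped level and any replacements.

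If pooling were really wanted, the threshold would have to rise to 5 (type I error .019 at 33, .026 at 36, .043 at 42), and the ORR would still mix dose levels.

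The cost is wording only. No dose or clinical rule changes. The downside is that the stated maximum enrolment becomes larger: 42 after two full de-escalations, before replacements.

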9.4 Statistical analyses

We will use intention to treat (ITT) analysis for the primary and secondary endpoints.

9.4.1 Efficacy analyses

Primary Endpoint: Overall response rate (ORR) by RECIST v1.1 criteria for combined therapy of olaparib and temozolomide.

Analytic Plan for Primary Endpoint:

The objective response is defined as a complete or partial response, as determined by investigator assessment using RECIST v 1.1 and confirmed by repeated assessment > 4 weeks after initial documentation. Patients with missing or no response assessments are classified as non-responders. The trial will terminate early if we do not observe 1 or more responses in the first 9 evaluable patients. The ORR will be estimated using the 95% confidence interval (CI) based on Wilson's method. A 5% 2-sided alpha will be used.

Secondary Endpoints: PFS, OS, Safety

Analysis Plans for Secondary Endpoints:

Secondary endpoints include overall survival, progression-free survival, and toxicity. Survival endpoints will be plotted using the Kaplan-Meier, product-limit method and compared across clinical measurements using Cox proportional hazards regression. Time to progression begins at the time of initial treatment and ends at the earliest of withdrawal, diagnosed progression, or death. For PFS subjects who are alive and have not progressed will be censored at the date of

their last RECIST tumor assessment. For OS subjects who are alive will be censored at the date of their last survival assessment. Toxicity rates will be compared to established rates for these treatments and summarized using means and 95% confidence intervals.

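### The ORR interval is a fixed-sample Wilson 95% interval, although the trial is two-stage with a stop at 0/9; its upper limit is too low, and at 4/30 its lower limit suggests stronger evidence than the design's one-sided .049

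*Combined protocol and SAP*

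**What the plan says.** Section 9.2 says that the primary endpoint "will be assessed in a Simon's two-stage optimal design". The null rate is 5%, and power is stated as 90% at a true 25%. The stage 1 rule is: "The trial will terminate early if we do not observe 1 or more responses in the first 9 evaluable patients". The null is rejected "if we observe 4 or more responses in the evaluable patient sample of 30". On the error rate: "The probability of 4 or more responses in a sample of 30 has probability .049, which is the significance level". That is an upper-tail probability, so the test is one-sided.

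Section 8.1 defines the ORR as the simple proportion of patients with a complete or partial response. Section 9.4.1 repeats the stop at 0/9 and continues: "The ORR will be estimated using the 95% confidence interval (CI) based on Wilson's method". It then sets alpha at 5%, two-sided. Neither section adjusts the interval for the stage 1 stop or says how the two-sided alpha relates to the one-sided .049.

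**The concern.** The test and the interval use different sample spaces. The .049 in section 9.2 is a two-stage probability. Wilson's interval treats 30 patients (or 9, after an early stop) as a sample whose size was fixed in advance.

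The ORR and its interval are what the trial will report. If the upper limit is too low, a modest result appears to rule out response rates that the design cannot rule out. If the 95% interval just clears 5% at the smallest positive result, a reader will take that as evidence at .025 one-sided. The two-sided alpha in section 9.4.1 encourages that reading.

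**Working it through.** **Inputs (section 9.2).** n1 = 9, stop at 0 responses; N = 30, reject at 4 or more; null 5%, alternative 25%. Let X1 be stage 1 responses and X total responses.

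**The plan's own figures.**
- Level: P(X1 ≥ 1, X ≥ 4) at 5% = .0489 (stated .049).
- Power: the same probability at 25% = .902 (stated 90%).
- Early stop at 5%: .95^9 = .630 (stated 63%).
- Expected N at 5%: 9 + 21 × (1 − .630) = 16.8 (stated 17).
- A fixed sample of 30 with the same cut-off would have level .061. So .049 is the two-stage value.

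**Wilson at 4/30**, with z = 1.96 and z² = 3.84.
- Centre: (4 + 1.92)/(30 + 3.84) = .175.
- Half-width: 1.96 × √(4 × 26/30 + .96)/33.84 = .122.
- Interval: 5.3% to 29.7%, width 24.4 points.

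**Two-stage exact interval at 4/30.** A stop at stage 1 ranks lowest, and results at 30 patients rank by total responses.
- Lower 95% limit solves P(X1 ≥ 1, X ≥ 4) = .025, giving 4.0%.
- Upper 95% limit solves 1 − P(X1 ≥ 1, X ≥ 5) = .025, giving 35.3%. Width is 31.3 points.
- With .05 per tail (a 90% interval): 5.04% to 31.3%.

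**Separating the two causes at 4/30.**

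| Method | Lower 95% | Upper 95% |
|---|---|---|
| Wilson, fixed sample | 5.3% | 29.7% |
| Clopper-Pearson, fixed sample | 3.8% | 30.7% |
| Exact, two-stage | 4.0% | 35.3% |

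From Wilson to fixed-sample exact, the lower limit falls below 5% and the upper limit moves by 1 point. From fixed-sample exact to two-stage exact, the upper limit rises by 4.6 points and the lower limit rises slightly. The exclusion of 5% is therefore due to Wilson being approximate, and the low upper limit is mainly due to ignoring the stop.

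**At 0/9.** Wilson's upper limit is z²/(9 + z²) = 3.84/12.84 = 29.9%. The two-stage exact limit solves (1 − p)^9 = .025, giving 33.6%. Fixed-sample exact on 9 patients gives the same 33.6%, so this gap is Wilson's approximation. It matters because the stopping rule puts real probability on this outcome.

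**Wilson 95% coverage under the two-stage design** (full enumeration).

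| True rate | Coverage | Probability lower limit is above the truth |
|---|---|---|
| 5% | .951 | .049 |
| 10% | .975 | .025 |
| 20% | .972 | .025 |
| 25% | .973 | .022 |
| 30% | .897 | .040 |

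At 30% the upper limit falls below the truth with probability .0625. Of that, .7^9 = .040 is the 0/9 stop; the rest is 1 to 4 responses of 30. The two-stage exact interval covers .983 there. Fixed-sample Wilson at 30% covers .930.

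**Neighbouring results.** At 3/30, Wilson is 3.5% to 25.6% and two-stage exact 2.4% to 34.1%; both include 5%. At 5/30, they are 7.3% to 33.6% and 5.8% to 37.4%; both exclude it. The two disagree about 5% only at 4/30.

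**Sidedness.** The two-stage upper-tail probability at 5% is .0489 for 4/30 and .0136 for 5/30. At .025 in the upper tail, 4/30 would not reject, which contradicts the rule in section 9.2.

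**The case against.** The best defence is that nothing the trial decides depends on the interval. The rule is a count, and Wilson happens to agree with it: the limit is below 5% at 3/30 and above it at 4/30. A 95% two-stage interval would include 5% at 4/30, where the plan rejects. Wilson is a named, prespecified and respectable method, and its coverage is nominal or better at the rates checked from null to alternative. All of this stands, and it limits the point to reporting. It does not answer the upper limit, the coverage at 30%, or the mismatch between the two statements of alpha.

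Three stronger readings are tempting, and the documents do not support them.
- *Ignoring the two stages is why 5% is excluded at 4/30.* It is not. Wilson's lower-limit error at 5% would be .061 in a fixed sample of 30 and is .049 here, so the futility stop reduces it.
- *The reported ORR is inflated.* Over all trials the raw rate is biased downward. Its bias is [9p + 21p(1 − (1 − p)^9)]/30 − p: −2.2 points at 5%, −2.7 at 10% and −1.3 at 25%.
- *The unbiased two-stage estimator (UMVUE) should therefore be the headline.* That is a trade-off. It gives 17.1% for 4/30 and 11.1% for 1/30. Its root mean squared error is higher than the raw rate's at 5% (.067 against .048) and 10% (.084 against .076), and lower at 25% (.096 against .101).

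**Conclusion.** The point holds as a low-cost improvement to reporting. Ignoring the stop makes the upper limit at 4/30 about 5 points too low on exact methods, and Wilson's approximation adds about 1 point. Coverage falls to about .90 at a true 30%. At 4/30 the 95% Wilson interval also suggests one-sided evidence at .025 where the design gives .049. Wilson is not too narrow in general, and the go/no-go decision does not change.

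These figures assume exactly 30 patients in the final ORR analysis, or 9 after a stop. The ORR set in section 9.3 also counts patients who died or stopped early, and section 9.2 allows non-evaluable patients to be replaced, so the denominator could exceed 30. With 4/31 Wilson's lower limit is 5.1%; with 4/32 it is 4.97% and no longer excludes 5%. The two-stage limits also depend on the stated ordering of outcomes, which should be written down.

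**What to change.** In section 9.4.1:
1. Prespecify a two-stage exact interval for the ORR, with the ordering stated (stage 1 stop lowest, then total responses). Give it at 90% two-sided, tied to the test, and at 95%.
2. Replace the two-sided 5% alpha with the one-sided level of section 9.2.
3. Keep the raw proportion as the headline estimate. Show the Wilson interval, and optionally the UMVUE, as supplementary lines.

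The cost is a few lines of analysis code, with no change to patients, data or design. The downside is a wider, more conservative interval, and a 95% interval that includes 5% at 4/30 although the rule rejects. For that reason the 90% interval, whose lower limit at 4/30 is 5.04%, should be the one linked to the test.
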